## **5.2. Concomitant Medications**

Subjects cannot receive any nonstudy anticancer therapy, hormonal therapy, or radiotherapy during the treatment period.

Use of hematopoietic growth factors, if required, are permitted in Cycle 1. In subsequent cycles, hematopoietic growth factors may be used for prophylaxis or treatment based on the clinical judgment of the Investigator.

Concomitant use of dietary supplements, medications not prescribed by the Investigator, and alternative/complementary treatments is discouraged, but not prohibited.

Please refer to package inserts for cetuximab, cisplatin, and carboplatin for additional information on use of concomitant medications.

All concomitant medication taken by subjects during the study must be recorded in the eCRF.

### **5.2.1. Patritumab**

Patritumab is contraindicated for subjects with known hypersensitivity to either the drug substance or inactive ingredients in the drug product. There are no known contraindications. Drug-drug interaction studies have not yet been conducted.

### **5.2.2. Cetuximab**

In combination with platinum-based chemotherapy, the frequency of severe leukopenia or severe neutropenia may be increased, and thus may lead to a higher rate of infectious complications such as febrile neutropenia, pneumonia, and sepsis compared to platinum-based chemotherapy alone.

### **5.2.3. Cisplatin**

#### **Nephrotoxic substances**

Concomitant administration of nephrotoxic (eg, cephalosporins, aminoglycosides, amphotericin B or contrast media) or ototoxic (eg, aminoglycosides) medicinal products will potentiate the toxic effect of cisplatin on the kidneys.

#### **Ototoxic substances**

Concomitant administration of ototoxic (eg, aminoglycosides, loop diuretics) medicinal products will potentiate the toxic effect of cisplatin on auditory function. Except for subjects receiving doses of cisplatin exceeding 60 mg/m^2, whose urine secretion is < 1000 mL per 24 hours, no forced diuresis with loop diuretics should be applied in view of possible damage to the kidney tract and ototoxicity.

#### **Weakened live vaccines**

Yellow fever vaccine is strictly contraindicated because of the risk of fatal systemic vaccinal disease. In view of the risk of generalized illness, it is advisable to use an inactive vaccine if available. Live/attenuated or inactivated influenza vaccine is allowed.

#### **Antihistamines, Phenothiazines and others:**

Simultaneous use of antihistamines, buclizine, cyclizine, loxapine, meclozone, phenothiazines, thioxanthenes or trimethobenzamines may mask ototoxicity symptoms (such as dizziness and tinnitus).

#### **Anticonvulsive substances**

Serum concentrations of anticonvulsive medicines may remain at subtherapeutic levels during treatment with cisplatin.

#### **Anti-epileptics**

In subjects receiving cisplatin and anticonvulsant agents, the serum level of the anticonvulsant agent might be reduced. This is probably due to reduced absorption and/or increased metabolism. In these subjects, the plasma levels of anticonvulsants should be monitored, and the dose adjusted accordingly. Prophylactic use of phenytoin or fosphenytoin is prohibited.

### **5.2.4. Carboplatin**

Concurrent therapy with nephrotoxic or ototoxic drugs such as aminoglycosides, vancomycin, capreomycin, and diuretics, may increase or exacerbate toxicity due to carboplatin induced changes in renal clearance.

Combination therapy with other myelosuppressive agents may require dose changes or rescheduling of doses in order to minimize the additive myelosuppressive effects.

Prophylactic use of phenytoin or fosphenytoin is prohibited.

Receiving yellow fever vaccine or live attenuated vaccines is prohibited.

## 6. STUDY PROCEDURES

A study visit schedule is provided in [Table 17.2](#). Study treatments should be administered as specified in [Section 3.1.2](#).

### 6.1. Screening

#### 6.1.1. Tissue Screening

Samples must be taken from subjects who have recurrent or metastatic disease (rec/met). These samples must be from either rec/met archived or fresh biopsy material. Samples can derive from either primary recurrent tumor or from its lymph nodal metastases originating from the oral cavity, oropharynx, hypopharynx, and larynx. No additional treatment is allowed between biopsy and study entry.

Tissue samples must be formalin fixed, paraffin embedded, slides cut of 5 microns, unstained and unbaked. Please refer to the laboratory manual for additional information on management of tissue samples.

The following procedures will be conducted:

- Obtain written consent from the subject to collect tissue or perform a biopsy
  - If a tumor biopsy is performed, record only SAEs directly related to the procedure.
- Samples will be analyzed for and must meet eligibility criteria:
  - HRG expression
  - HPV status or p16 is required. These results may be obtained from either a local lab or samples sent to the central lab

#### 6.1.2. Screening (Up to 14 Days Before the First Dose of Study Treatment Unless Otherwise Noted)

Screening procedures can be done at the same time as tissue screening (Section 6.1.1) at the discretion of the Investigator.

The following activities and/or assessments will be performed at/during screening (within 14 days before the first dose of study treatment [unless otherwise noted]):

- Obtain signed informed consent
- Obtain signed informed consent for pharmacogenomics (optional)
- Evaluation of inclusion and exclusion criteria
- Confirm results of the HRG expression level and HPV or p16 status.
- Record demographic and medical history information
  - Including smoking history

- Record AEs and concomitant medications
- Perform a physical examination, including vital sign measurements, blood pressure, heart rate, temperature, weight, and height. Height will be measured only at Screening
- Assess functional status using the ECOG Performance Status Scale (Section 10.1)
- Perform an echocardiogram or multigated acquisition (MUGA) scan (the same test must be used for a subject throughout the study) (Section 9.11.1)
- Perform a 12-lead ECG
- Collect blood sample for complete blood count (CBC) (Section 9.7)
- Collect blood sample for coagulation-only at Screening (Section 9.7)
- Collect blood sample for serum chemistry (Section 9.7)
- Obtain urine sample for urinalysis (Section 9.7)
- Perform a serum or urine pregnancy test for female subjects of childbearing potential (must be confirmed negative before dosing). Additional pregnancy testing may be done at the discretion of the Investigator and/or if required by local regulations for women of child-bearing potential (Section 9.7)
- Perform radiographic tumor assessments after eligibility is determined. Existing radiographic scans can be used for the baseline evaluation if the scans were performed within 4 weeks prior to randomization. Computed tomography (CT) and/or magnetic resonance imaging (MRI) (spiral CT or MRI with  $\leq 5$  mm cuts) should be used for tumor assessment unless another modality of radiographic disease assessment is necessary for the lesions per RECIST guidelines Version 1.1, (see Appendix 17.3)

### 6.1.3. Randomization

For subjects who are eligible to participate in the study, complete the following:

- Randomize subject in the IxRS
- Study treatment should begin within 3 business days after randomization

## 6.2. Treatment Period

A hospital overnight stay associated with study procedures or treatment is allowed and will not be reported as an SAE (see Section 9.4.2).

Additional pregnancy testing may be done during the treatment period at the discretion of the Investigator and/or if required by local regulations for women of child-bearing potential.

### 6.2.1. Cycle 1: Week 1, Day 1

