## **9. SAFETY ASSESSMENTS**

### **9.1. Adverse Events**

All clinical AEs occurring after the subject signs the Informed Consent Form for general study participation and up to 40 days after the last dose of any study drug administered, whether observed by the investigator or reported by the subject, will be recorded on the Adverse Event CRF page. Medical conditions (including laboratory values/vital signs that are out of range) that were diagnosed or known to exist prior to Informed Consent will be recorded as part of medical history.

All AEs, SAEs, and events of special interest are to be reported according to the procedures in Section 9.5.

Any laboratory findings should be appraised by the investigator as to clinical significance. An isolated abnormal laboratory result (ie, not related to a reported diagnosis) should be reported as an AE if it is symptomatic, leads to study drug reduction or discontinuation, requires corrective treatment, or is defined as an AE of Special Interest in Section 9.3.

At each visit, the investigator will determine whether any AEs have occurred by evaluating the subject. Adverse events may be directly observed, reported spontaneously by the subject or by questioning the subject at each study visit. Subjects should be questioned in a general way, without asking about the occurrence of any specific symptoms. The Investigator must assess all AEs to determine seriousness, severity, and causality, in accordance with the definitions in Section 9.4. The Investigator's assessment must be clearly documented in the site's source documentation with the Investigator's signature.

Always report the diagnosis as an AE or SAE term. When a diagnosis is unavailable, report the primary sign or symptom as the AE or SAE term with additional details included in the narrative until the diagnosis becomes available. If the signs and symptoms are distinct and do not suggest a common diagnosis, report them as individual entries of AE or SAE. For events that are serious due to hospitalization, the reason for hospitalization must be reported as the SAE (diagnosis or symptom requiring hospitalization). A procedure is not an AE or SAE, but the reason for the procedure may be an AE or SAE. Pre-planned (prior to signing the Informed Consent Form) procedure or treatment requiring hospitalization for pre-existing conditions which do not worsen in severity should not be reported as SAEs (see Section 9.4 for Definitions).

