### **9.4.2. Serious Adverse Event**

Any untoward medical occurrence that at any dose:

- Results in death

- Is life-threatening
- Requires inpatient hospitalization or prolongation of existing hospitalization
- Results in persistent or significant disability/incapacity
- Is a congenital anomaly/birth defect, or
- Is an important medical event

Note: The term “life-threatening” in the definition of “serious” refers to an event in which the subject was at risk of death at the time of the event; it does not refer to an event which hypothetically might have caused death if it were more severe.

Medical and scientific judgment should be exercised in deciding whether expedited reporting is appropriate in other situations, such as important medical events that may not be immediately life-threatening or result in death or hospitalization but may jeopardize the subject or may require intervention to prevent one of the other outcomes listed in the definition above. Examples include allergic bronchospasm, convulsions, and blood dyscrasias, or development of drug dependency or drug abuse.

Note:

- A procedure is not an AE or SAE, but the reason for the procedure may be an AE or SAE
- Pre-planned (prior to signing the Informed Consent Form) procedures or treatment requiring hospitalizations for pre-existing conditions which do not worsen in severity are not SAEs

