### **9.5. Safety Reporting – Procedure for Investigators**

All AEs, SAEs, and events of special interest will be reported in the eCRF. In addition, the Investigator should report the following types of events on a SAVER form within 24 hours of becoming aware of them:

- SAEs (see Section 9.4.2)
- Hepatic events, both serious and nonserious, presenting with combination abnormalities meeting criteria for a potential “Hy’s law” case (ie, ALT or AST  $\geq 3 \times$  ULN, with simultaneous total bilirubin  $> 2 \times$  ULN; see Section 9.3.1)

All events (serious and nonserious) must be reported with the Investigator’s assessment of the event’s seriousness, severity, and causal relationship to study drug. A detailed narrative summarizing the course of the event, including its evaluation, treatment, and outcome should be provided. Specific or estimated dates of event onset, treatment, and resolution should be included when available. Medical history, concomitant medications, and laboratory data that are relevant to the event should also be summarized in the narrative. For fatal events, the narrative should state whether an autopsy was or will be performed, and should include the results if available. Source documents will be retained in site’s files and should not be submitted to the Sponsor for SAE reporting purposes.

Urgent safety queries must be followed up and addressed promptly. Follow-up information and response to non-urgent safety queries should be combined for reporting to provide the most complete data possible within each follow-up.

Please call the local SAE Hotline number (Section 15.2.1.5) or your study monitor for any questions on SAE reporting.

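### Section 6.2 exempts overnight stays from SAE reporting without any qualifier and cites Section 9.4.2, which contains no such exemption

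*Protocol*

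**What the plan says.** Protocol Section 6.2 (Treatment Period) opens the visit-by-visit instructions with this rule: "A hospital overnight stay associated with study procedures or treatment is allowed and will not be reported as an SAE (see Section 9.4.2").

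Section 9.4.2, to which it points, lists among the criteria that make an untoward medical occurrence serious: "Requires inpatient hospitalization or prolongation of existing hospitalization". Two notes in that section bear on hospital stays:

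- On procedures: "A procedure is not an AE or SAE, but the reason for the procedure may be an AE or SAE".
- On planned admissions: "Pre-planned (prior to signing the Informed Consent Form) procedures or treatment requiring hospitalizations for pre-existing conditions which do not worsen in severity are not SAEs".

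Section 9.1 adds a reporting instruction: "For events that are serious due to hospitalization, the reason for hospitalization must be reported as the SAE".

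Section 9.5 states that "All AEs, SAEs, and events of special interest will be reported in the eCRF", and that SAEs must also go on a SAVER form within 24 hours of the investigator becoming aware of them.

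SAP Section 8.3.1 tabulates treatment-emergent SAEs overall and by relationship to patritumab, cetuximab and cisplatin/carboplatin (Tables 15.3.1.3 and 15.3.1.7 to 15.3.1.9).

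**The concern.** The Section 6.2 sentence sets one condition, association with study procedures or treatment. An admission caused by a treatment toxicity meets that condition as readily as an admission for hydration. The sentence does not separate a stay arranged for convenience from a stay that an adverse event made necessary, and the section it cites does not supply the distinction in the form of an overnight-stay exemption.

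Two things depend on the seriousness classification. One is the expedited route: an event not classed as serious has no 24-hour SAVER report unless it meets the separate potential Hy's law criterion in Section 9.5. The other is the set of treatment-emergent SAE tables, which count only events classed as serious. Sites that follow Section 6.2 literally and sites that follow Sections 9.1 and 9.4.2 would classify the same admission differently. With approximately 105 subjects at approximately 35 sites, the average is 105 / 35 = 3 subjects per site, too few for such a difference between sites to show up in the data.

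**Working it through.** No calculation applies. The check is a comparison of the texts.

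1. **Scope of the Section 6.2 exemption.** It covers an overnight stay linked to study procedures or treatment. It has no condition that the stay be planned in advance and none that an adverse event be absent.

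2. **Whether Section 9.4.2 contains it.** It does not. The hospitalization criterion has no carve-out for overnight stays. The only hospitalization exemption is limited in three ways: planned before consent, for a pre-existing condition, and without worsening. A stay for study treatment is not that. The note on procedures makes the answer turn on the reason for the procedure, a test that Section 6.2 leaves out.

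3. **Whether Section 9.1 agrees with Section 6.2.** Only on a narrow reading of Section 6.2. Section 9.1 requires the diagnosis or symptom behind a hospitalization that makes an event serious to be reported as the SAE.

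4. **Where the rules part.** Four stays, taken under each text:

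| Stay | Section 6.2 as worded | Sections 9.1 and 9.4.2 |
|---|---|---|
| Hydration after cisplatin, no adverse event | Not an SAE | Not an SAE: no untoward occurrence |
| Stay for the 24-hour PK sample, no adverse event | Not an SAE | Not an SAE: no untoward occurrence |
| One-night admission because of an infusion reaction | Exempt, if taken as associated with treatment | SAE if inpatient hospitalization was required; the reaction is the reported term |
| Planned hydration stay prolonged by vomiting | Unclear; exempt if the whole stay is taken as associated with treatment | SAE through the prolongation criterion |

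The texts agree on the first two rows. They can part on the last two, and the documents do not say which section then prevails.

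5. **Whether the third row is foreseeable.** It is. Protocol Section 5.1.7.2 says severe cetuximab infusion reactions may be common and that symptoms can appear up to several hours after the infusion. Section 5.1.7.1 requires subjects with severe patritumab/placebo infusion reactions to be monitored until signs and symptoms have fully resolved. Section 8.1 puts the intensive-PK dosing day, with hydration, at about 7 hours. A reaction late on that day could plausibly lead to a night in hospital.

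6. **What is lost if Section 6.2 is applied literally.** The AE record is kept under Section 9.5, and the event is still tabulated by worst CTCAE grade under SAP Section 8.3.1. The serious classification, the 24-hour SAVER report and the entry in the treatment-emergent SAE tables are not kept.

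**The case against.** The best defence is that the sentence was never about toxicity. It says the stay is allowed, which fits elective stays; nobody needs permission to admit a sick patient. Its subject is the stay, not an event, and it sits in the visit schedule, not in the safety-reporting chapter. The protocol supplies ordinary reasons for such stays: hydration and urine output to be maintained for 24 hours after cisplatin (Section 3.1.2.1) and a 24-hour sample in the intensive PK substudy (Section 6.2.2). A reader who follows the pointer to Section 9.4.2 finds that an SAE must be an untoward medical occurrence, which a hydration stay is not. Section 9.1 then covers admissions caused by an event. Section 9.4.2 also has an important-medical-event criterion that does not depend on hospitalization, with allergic bronchospasm and blood dyscrasias among its examples.

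Most of this stands. The logistic intent is the likely one, and some reactions would be serious on another criterion. But intent that is left unwritten does not bind a site, and the wording as it stands reaches further. The mandatory rule in Section 9.1 does not cure the conflict; it is one side of it.

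A reader might infer that the plan lets toxicities go unrecorded, or that it exempts toxicity admissions on purpose. The documents support neither. Section 9.5 keeps every AE in the eCRF, and Sections 9.1 and 9.4.2 still require the event behind a hospitalization to be reported as serious. Nor does anything say that the Data Monitoring Committee looks at SAEs alone; Protocol Section 11.9 has it review accumulating safety data generally.

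**Conclusion.** The point holds as an inconsistency in a safety-reporting rule. Section 6.2 is unqualified, its cross-reference does not support it, and read as written it conflicts with Sections 9.1 and 9.4.2. The consequence is possible under-classification: an event that is serious only because of a one-night hospital stay could be recorded as non-serious, without a 24-hour SAVER report and outside the treatment-emergent SAE tables.

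No size can be given. The documents contain no SAE rates, no share of SAEs serious only through hospitalization, and no frequency of overnight stays. The effect ranges from nil, if all sites read the sentence narrowly, to some unknown share of such events. Any percentage would be the product of assumptions with no anchor in the plan.

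The conclusion assumes that at least one site might apply the sentence literally. It does not touch the primary PFS analysis or any hypothesis test; safety analysis here is descriptive. The text should be corrected all the same, because it is a stated rule that gives the wrong classification when followed as worded.

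**What to change.** Reconcile Section 6.2 with Sections 9.1 and 9.4.2. Suggested text for Section 6.2:

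> An overnight stay solely for planned study procedures, study drug administration, hydration or PK sampling, where no adverse event is the reason for the stay or for its prolongation, is not an SAE. If an adverse event makes a stay or its prolongation necessary, that event is reported under Sections 9.1 and 9.4.2.

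Add the same exemption to the notes in Section 9.4.2, so that the cross-reference is correct.

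The cost is a reworded rule in Section 6.2 and one added note in Section 9.4.2. No data, visits, analyses or clinical management change.

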#### Pre-dose

- Perform a physical examination
  - Weight measured within 3 days prior to Day 1 may be used to calculate the drug dose
- Vital sign measurements (blood pressure, heart rate, temperature)
- Assess functional status using the ECOG Performance Status Scale (Section 10.1).
- Record AEs
- Record concomitant medications
- Have subject complete the PRO assessments before any study-related procedures are performed
- Collect blood sample for CBC (Section 9.7)-within 3 days prior to visit
- Collect blood sample for serum chemistry (Section 9.7)-within 3 days prior to visit
- Collect blood sample for HAHA-within 3 days prior to visit (Section 8.4 and Table 8.1)
- Collect blood sample for sparse PK (Table 8.1)
- Collect blood sample for pharmacogenetics (PGx) (optional)
- Collect blood samples for additional biomarkers

#### Study Treatment

Information for dosing and administration is found in Section 3.1.2 . Study drugs should be administered consecutively in the order below:

- Administer patritumab IV as specified in Section 3.1.2
- Administer cetuximab IV as specified in Section 3.1.2
- Administer cisplatin (or carboplatin) IV one hour after cetuximab, as specified in Section 3.1.2.

#### End of Patritumab, Cetuximab, and Cisplatin or Carboplatin Infusions

- Perform vital sign measurement
- Record concomitant medications and AEs throughout administration of study drugs
- Sparse PK: collect a blood sample for PK at end of patritumab infusion (EOI) at 1 hr  $\pm$  10 min for all subjects (Table 8.1)
- Intense PK substudy

- Collect blood sample for PK at 3 hrs  $\pm$  10 min after start of patritumab infusion (approximately EOI for cetuximab) (Table 8.2)
- Collect blood sample for PK at 4 hrs  $\pm$  10 min after start of patritumab infusion (or 4.25 hrs  $\pm$  10 min, approximately EOI for carboplatin for those subjects receiving carboplatin) (Table 8.2)
- Collect blood sample for PK at 5 hrs  $\pm$  10 min after start of patritumab infusion) (approximately EOI for cisplatin for those subjects receiving cisplatin) (Table 8.2)
- Collect blood sample for PK at 6 hrs  $\pm$  10 min after start of patritumab infusion (Table 8.2)
- Collect blood sample for PK at 7 hrs  $\pm$  10 min after start of patritumab infusion (Table 8.2)

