#### 3.1.2.1. Treatment Administration

[Figure 3.2](#) illustrates the order and timing of the treatments involved.

- Patritumab initial loading dose is 18 mg/kg IV (or placebo) over 60 minutes ( $\pm 10$  minutes) followed in cycle 2 and beyond with a maintenance dose of 9 mg/kg IV over 60 minutes ( $\pm 10$  minutes) every three weeks
  - Infusion time can be extended to a maximum of 120 minutes for subjects unable to tolerate the 60 minute infusion
- Cetuximab initial dose at 400 mg/m^2 IV as a 2-hour infusion followed by 250 mg/m^2 over 60 minutes weekly

One hour after the end of the cetuximab administration (on the weeks when cetuximab and platinum therapy are coadministered) infuse with either:

- Cisplatin at 100 mg/m^2 IV infused over 1 hour, every three weeks up to a maximum of 6 cycles
  - Pretreatment hydration with 2 liters of fluid prior to a cisplatin infusion is recommended and should adhere to institutional standards. Adequate hydration and urinary output must be maintained during the following 24 hours. Other pretreatments such as anti-emetic prophylaxis and post-treatments such as hydration are up to the discretion of the Investigator
  - This can be given in a separate infusion during patritumab and cetuximab infusion

[figure not shown]
OR

- Carboplatin, IV bolus over 30-60 minutes, every 3 weeks for a maximum of 6 cycles. The carboplatin dose will be calculated using the Calvert formula:
  - AUC 5 is the target
  - Carboplatin Dose (mg) = 5 x (glomerular filtration rate [GFR] + 25)
  - Estimated serum creatinine clearance (mL/min) calculated using the modified Cockcroft-Gault equation ([Appendix 17.1](#)) can also be used as an estimate for GFR

- The carboplatin dose is required to be re-calculated for every dosing based on the current GFR (or creatinine clearance as an estimate of GFR as per the protocol).
- Pre- and post-treatments are up to the discretion of the investigator

Note: It is important to use the infusion times given above for cisplatin and carboplatin; however, different infusion durations may be used if local practice dictates otherwise, except during Cycle 1, Day 1 for those subjects participating in the Intense PK sampling.

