**6.2.4. Cycle 1: Week 2, Day 8**

- Physical examination
- Vital signs
- ECOG Performance Status
- Record concomitant medications and AEs
- Blood samples for CBC (hematology with differential and platelet count), (Section 9.7)-may be collected within 3 days prior to visit
- Serum chemistries-may be collected within 3 days prior to the visit
- Intense PK substudy: collect blood sample for PK at 168 hrs  $\pm$  24 hrs (Table 8.2)-within 3 days prior to visit
- Administer cetuximab IV (infused weekly) as specified in Section 3.1.2 (given on Day 8 and Day 15 of all cycles)

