**Table 8.2: Sub Study: Intensive PK Assessments Relative to the Start of Patritumab Infusion at Cycle 1 [n = 30]**

Study Treatment	Pre-inf	Day 1						Day 2	Day 3	Day 8	Day 15	Day 21
		1 h (EOI) $\pm$ 10 min	3 h $\pm$ 10 min	4 h $\pm$ 10 min	5 h $\pm$ 10 min	6 h $\pm$ 10 min	7 h $\pm$ 10 min	24 h $\pm$ 1 h	48 h $\pm$ 1 h	168 h $\pm$ 24 h	336 h $\pm$ 24 h	504 h $\pm$ 24 h
Patritumab	X	X	X	X	X	X	X	X	X	X	X	X
Cetuximab	X		EOI	X	X	X	X	X	X	X		
Cisplatin	X				EOI	X	X	X	X			
or												
Carboplatin	X			4.5 h EOI	X	X	X	X	X			

Pre-inf = Preinfusion, EOI = End of infusion, h = hours, min = minutes.

Note: One blood sample to produce 3 mL of serum sample will be collected at each time point. The resulting serum will be divided into 3 aliquots of 1 mL for analysis of each analyte depending on the dose regimen. Further details will be provided in the lab manual.

Patritumab will be infused over 1 hour followed by cetuximab infused over 2 hours (end of infusion at  $\sim$ 3 h) and then a 1 h pause ( $\sim$ 4 h). Then cisplatin will be infused over 1 hour (end of infusion  $\sim$ 5 h) or carboplatin infused over 30-60 minutes (end of infusion  $\sim$ 4.5 h). Subjects will remain in the clinic for hydration following cisplatin/carboplatin

infusions for approximately 2 hours following infusions to complete hydration (ie, ~7 h in total). Only one blood sample will be collected at each scheduled time point and the resulting serum will be aliquoted for each analyte. Blood collection should approximately correspond to EOI of each drug as listed, at the nominal times defined relative to the start of patritumab infusion.

Serum concentrations of patritumab, cetuximab, and platinum will be measured, as appropriate, using validated assays. Specific instructions for collection and shipping of PK samples will be provided in the Laboratory Manual.

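### Intensive PK times in Protocol Section 6.2 disagree with Table 8.2: the carboplatin end-of-infusion sample is set at 4.25 h rather than 4.5 h, and the Day 8 sample carries two incompatible windows.

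*Protocol*

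**What the plan says.** **Carboplatin sample.** The intensive PK bullets in Protocol Section 6.2.1 ask for a sample at 4 h ± 10 min after the start of patritumab. For carboplatin recipients they give 4.25 h ± 10 min instead, described as "approximately EOI for carboplatin for those subjects receiving carboplatin", with a reference to Table 8.2.

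Table 8.2 marks the carboplatin end of infusion (EOI) at 4.5 h. The text below it builds the timeline: "Patritumab will be infused over 1 hour followed by cetuximab infused over 2 hours", then a one-hour pause, then "or carboplatin infused over 30-60 minutes (end of infusion" at about 4.5 h). The same text states the purpose of the schedule: "Blood collection should approximately correspond to EOI of each drug as listed, at the nominal times defined relative to the start of patritumab infusion". The SAP shell for Figure 15.4.1.5 also plots carboplatin at 4.5 h.

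Section 3.1.2.1 lets sites vary platinum infusion durations by local practice, "except during Cycle 1, Day 1 for those subjects participating in the Intense PK sampling".

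**Day 8 sample.** The PK bullet in Section 6.2.4 gives 168 h ± 24 h, cites Table 8.2, and ends with a second condition: "Table 8.2)-within 3 days prior to visit". Table 8.2 has only the ± 24 h window.

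**Use of the data.** The protocol synopsis lists Cmax at EOI and AUC for patritumab, cetuximab and platinum as secondary endpoints in the PK subgroup. SAP Section 8.4.2 compares log-transformed AUClast and Cmax of cetuximab and platinum between arms by ANOVA, with 90% CIs for the geometric mean ratio.

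**The concern.** Section 6.2.1 cites Table 8.2 but gives a different clock time. A site working from the visit-by-visit text would draw about 15 minutes into the carboplatin infusion. That value would then fill the column headed End of Infusion in SAP Table 15.4.1.5. If the infusion is short, no later sample falls at its end, so the maximum observed concentration is too low.

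The Day 8 bullet contradicts itself if its last phrase is taken as permission. Day 8 is the last scheduled cetuximab sample in Table 8.2, so an early draw shortens the interval over which cetuximab AUClast is computed, for some subjects and not for others.

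Sites following Section 6.2 and sites following Table 8.2 would collect blood at different times under the same nominal label.

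**Working it through.** **Inputs**
- Patritumab 1 h, cetuximab 2 h, pause 1 h, carboplatin 30–60 min: Section 8.1, text below Table 8.2. Section 6.2.1 confirms the pause: "Administer cisplatin (or carboplatin) IV one hour after cetuximab, as specified in Section 3.1.2".
- Patritumab infusion tolerance ± 10 min: Section 3.1.2.1.
- Carboplatin EOI sample: 4.25 h ± 10 min (Section 6.2.1); 4.5 h (Table 8.2).
- Day 8 sample: 168 h ± 24 h (Table 8.2 and Section 6.2.4), plus the three-day phrase (Section 6.2.4 only).

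**Step 1: the plan's 4.5 h figure**
- Carboplatin start = 1 + 2 + 1 = 4.0 h.
- EOI = 4.0 + 0.5 = 4.5 h for 30 min, and 4.0 + 1.0 = 5.0 h for 60 min.

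Table 8.2's 4.5 h is reproduced, but only for a 30-minute infusion.

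**Step 2: the 4.25 h sample**
- Window = 4.25 ± 10/60 = 4.083 to 4.417 h.
- Latest allowed draw to earliest nominal EOI: 4.5 − 4.417 = 0.083 h = 5 min. To the latest nominal EOI: 5.0 − 4.417 = 0.583 h = 35 min.
- Share of a 30-minute infusion given at 4.25 h: 0.25/0.5 = 50%. Of a 60-minute infusion: 0.25/1.0 = 25%.
- For a 60-minute infusion the nominal EOI of 5.0 h coincides with the scheduled 5 h sample. For a 30-minute infusion that sample comes 30 minutes after the end.

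**Step 3: sensitivity to the patritumab tolerance (30-minute carboplatin)**

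| Patritumab | Carboplatin start | EOI | In 4.083–4.417 h? |
|---|---|---|---|
| 50 min | 3.833 h | 4.333 h | yes |
| 60 min | 4.000 h | 4.500 h | no |
| 70 min | 4.167 h | 4.667 h | no |

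**Step 4: size of the Cmax shortfall.** The documents give no platinum half-life, so this is an assumption: one compartment, constant-rate input over 30 min, half-life 1 to 6 h, k = ln 2 / half-life. With t in hours from the start of carboplatin, C(t) is proportional to 1 − exp(−kt) during infusion, and falls by exp(−k(t − 0.5)) afterwards.

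| Half-life | 4.25 h vs EOI | 4.417 h vs EOI | 5 h vs EOI |
|---|---|---|---|
| 1 h | 0.543 | 0.856 | 0.707 |
| 2 h | 0.522 | 0.845 | 0.841 |
| 3 h | 0.514 | 0.841 | 0.891 |
| 6 h | 0.507 | 0.837 | 0.944 |

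Observed Cmax is the larger of the two samples. With a draw at 4.25 h that is the 5 h value, 71% to 94% of the true EOI concentration.

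**Step 5: Day 8**
- Table 8.2 window: 168 ± 24 = 144 to 192 h.
- Three days before a visit at 168 h: 168 − 72 = 96 h, which is 144 − 96 = 48 h before the window opens.
- The nominal sampling interval would be shorter by 72/168 = 43%. The loss in AUClast cannot be derived from the documents, because it depends on the concentration profile.

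**Step 6: between-arm ratio.** If both arms' Cmax is understated by the same factor r, log(rA) − log(rB) = log A − log B. The geometric mean ratio is unchanged.

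**Step 7: a second timeline.** Table 17.2 footnote o puts cetuximab 60 minutes after patritumab administration. If that means a gap after the infusion ends, carboplatin starts at 1 + 1 + 2 + 1 = 5 h and ends at 5.5–6.0 h, and none of the nominal cetuximab and platinum EOI times hold.

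**The case against.** The best defence is that these are drafting slips which the rest of the protocol corrects. The 4.25 h bullet says approximately, cites the table that prints 4.5 h, and sits beside an instruction to match EOI. The 4.25 h and 4.5 h windows overlap if the same ± 10 min applies (4.33–4.42 h), and with a 50-minute patritumab infusion a 30-minute carboplatin infusion ends inside the 4.25 h window. On Day 8, the two conditions can be read jointly as 144–168 h, with no breach. Table 17.2 attaches its three-day footnote to the predose intensive PK sample but not to Day 8, and the Day 15 PK bullet has no such phrase. The wording resembles the CBC and chemistry bullets just above it.

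Much of this stands, and it rules out stronger readings that a reader might infer:
- **That the peak is missed for every carboplatin infusion.** It is not: the 5 h sample covers a 60-minute infusion, so the 25% figure does not imply a lost peak.
- **That all 30 PK subjects have a faulty Cmax.** Only carboplatin recipients are exposed. Platinum is the investigator's choice, and their number is not given.
- **That the protocol plainly authorises a 96 h draw.** That is one reading, and it assumes the Day 8 visit falls at 168 h.
- **That the drug-interaction comparison is biased.** Both blinded arms share the schedule, so the documents give no reason for mistiming to differ by arm.

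The objection does not remove the conflict. A site cannot follow both 4.25 h and 4.5 h as nominal times. Local infusion practice is ruled out as an explanation for this subset on Cycle 1 Day 1.

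**Conclusion.** Both contradictions are real, and both are minor. On nominal timing the Section 6.2.1 carboplatin sample precedes the end of infusion by at least 5 minutes even when drawn at the limit of its window. For infusions ending well before 5 h this understates observed Cmax. For a 30-minute infusion sampled at 4.25 h, the result is about 71–94% of the true EOI value under the assumed half-life of 1–6 h. The Day 8 bullet, read as an allowance, admits a draw 48 h before the Table 8.2 window opens.

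The consequence is understated absolute exposure and extra noise in a small PK comparison, not between-arm bias. The primary PFS analysis, its error rates and the sample size are unaffected.

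The conclusion rests on the Section 8.1 timeline holding as written and on the Day 8 visit falling at 168 h. Footnote o puts the first of these in doubt, so the passages must be reconciled together.

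**What to change.** 1. **Section 6.2.1:** replace the 4.25 h clock time with the actual end of the carboplatin infusion. State the nominal value as 4.5 h for a 30-minute infusion, and say that for a 60-minute infusion the 5 h sample serves as EOI. Record actual infusion and sampling times.
2. **Table 8.2 and SAP shells:** Table 8.2 lists only 4.5 h, so add the 60-minute case there and carry it into the SAP carboplatin table and figure shells.
3. **Section 6.2.4:** remove the three-day allowance from the PK bullet, keep the Table 8.2 window, and state that the sample is drawn before the Day 8 cetuximab infusion. Without that condition, a draw up to 192 h could follow the next dose and still be in window.
4. **Timeline:** reconcile Section 8.1 with Table 17.2 footnote o on the interval between patritumab and cetuximab, then confirm the nominal sample times. Which interval applies is for the sponsor to settle.

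The cost is wording in the protocol, laboratory manual and SAP shells. No samples are added; for a 60-minute infusion the EOI and 5 h draws are the same sample.
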